**2. PVR  $\geq 200$  mL and < 350 mL**

If a PVR of  $\geq 200$  mL but < 350 mL is identified at any post-treatment visit, the investigators/subinvestigators will assess the subject for any spontaneously reported associated

symptoms (such as voiding difficulties or bladder fullness in patients who have sensation), with the resulting action to be as follows:

- a. If a subject reports associated symptoms that in the opinion of the investigators/subinvestigators require CIC to be initiated, then CIC should be initiated and managed according to the Guidance about the Management of PVR Urine Volume.
- b. If a subject does not report any associated symptoms or if they report associated symptoms that, in the opinion of the investigators/subinvestigators, do not require CIC, the subject will be seen at an additional visit 1 week later, when the PVR and any associated symptoms will be reassessed. In addition, a urine analysis with a urine reagent strip as well as urinalysis, urine culture, and sensitivity test at the central laboratory will be performed. Based on the test results at this visit, the following procedures will be conducted:
  - 1) If the PVR is increasing and is associated with symptoms, that in the opinion of the investigators/subinvestigators require CIC, then CIC should be initiated and managed according to the Guidance about the Management of PVR Urine Volume.
  - 2) If the PVR is  $\geq 350$  mL then CIC should be initiated and managed according to the Guidance about the Management of PVR Urine Volume.
  - 3) If the PVR is increasing but is not associated with symptoms or is associated with symptoms that in the opinion of the investigators/subinvestigators do not require CIC, then the subject will be seen 1 week later to determine if CIC has become warranted based on PVR and/or any associated symptoms. The following procedures will be conducted at this additional visit:
    - A urine reagent strip, and urinalysis, urine culture and sensitivity test at the central laboratory will be collected.
    - If the investigators/subinvestigators judge that CIC should be initiated, then CIC should be initiated and managed according to the Guidance about the Management of PVR Urine Volume.
    - If CIC is not initiated and PVR continues to increase, the investigators/subinvestigators will determine whether the subject will be followed at regularly scheduled study visits or whether additional visits should occur.

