### Phase III-IV liver chemistry increased monitoring criteria with continued therapy

Liver Chemistry Increased Monitoring Criteria – Liver Monitoring Event	
Criteria	Actions

ALT <math>\geq</math>5xULN and <8xULN and bilirubin <2xULN without symptoms believed to be related to liver injury or hypersensitivity, and who can be monitored weekly for 2 weeks.
 
OR
 
ALT <math>\geq</math>3xULN and <5xULN and bilirubin <2xULN without symptoms believed to be related to liver injury or hypersensitivity, and who can be monitored weekly for 4 weeks.
	
 
• Notify the GSK medical monitor within 24 hours of learning of the abnormality to discuss subject safety.
 
• Subject can continue study treatment
 
• Subject must return weekly for repeat liver chemistries (ALT, AST, alkaline phosphatase, bilirubin) until they resolve, stabilise or return to within baseline
 
• If at any time subject meets the liver chemistry stopping criteria, proceed as described above
 
• If ALT decreases from ALT <math>\geq</math>5xULN and <8xULN to <math>\geq</math>3xULN but <5xULN, continue to
 

	
monitor liver chemistries weekly.
 

• If, after 4 weeks of monitoring, ALT <3xULN and bilirubin <2xULN, monitor subjects twice monthly until liver chemistries normalize or return to within baseline.

--	---

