8. SAFETY ANALYSES

The safety analyses will be based on the “Safety” population, unless otherwise specified. In detail, each Safety population will be used for each study phase as below table. In principle, summaries for TC1 will be only by treatment group, and summaries for GTC1, GTC2, GTC3 and Overall will be by treatment group and its total.

For AEs:

Study phase	Population	Summary Group
TC1	SPDB	By treatment group
GTC1	SP1	By treatment group and total
GTC2	SP2	By treatment group and total
GTC3	SP3	By treatment group and total
Overall	SP1	By treatment group and total

NOTES:

- The definition of population is described in [Analysis Populations](#).

For other than AEs:

Study phase	Population	Summary Group
TC1	SPDB	By treatment group
GTC1, GTC2, GTC3	SP1	By treatment group and total

NOTES:

- The definition of population is described in [Analysis Populations](#).

Safety data from unscheduled visit will not be included in safety analysis (but included in listing), and the safety data at last visit will be treated as Study Exit in safety analyses (but treated as Withdrawal in listing).

Visit displayed in safety analyses will be summarized below table for study phases and endpoints. SPDB (for TC1) and SP1 (for GTC1, GTC2 and GTC3) will be used for these summaries. Separate displays will be provided for TC1 and for GTCs (GTC1, GTC2 and GTC3).

Endpoints	Study phase	Study visit displayed in safety analyses table
Vital Sign	TC1	Baseline, Week 2, Week 6, Week 12, Week 24, Week 36, Study exit
	GTC1	Study baseline, Qualification for GTC1[1], Week 0 [1], Week 2, Week 6, Week 12, Week 24, Week 36, Study exit
	GTC2	Qualification for GTC2, Week 0, Week 2, Week 6, Week 12, Week 24, Study exit
	GTC3	Qualification for GTC3, Week 0, Week 2, Week 6, Week 12, Study exit
Clinical laboratory (chemistry and hematology), ECG	TC1	Baseline, Week 12, Study exit
	GTC1	Study baseline, Qualification for GTC1 [1], Week 12, Study exit

Endpoints	Study phase	Study visit displayed in safety analyses table
	GTC2	Qualification for GTC2, Week 12, Study exit
	GTC3	Qualification for GTC3, Week 12, Study exit
Body Weight	TC1	Baseline, Study exit
	GTC1	Study baseline, Qualification for GTC1 [1], Study exit
	GTC2	Qualification for GTC2, Study exit
	GTC3	Qualification for GTC3, Study exit
PVR	TC1	Baseline, Week 2, Week 6, Week 12, Week 24, Week 36, Study exit
	GTC1	Study baseline, Qualification for GTC1 [1], Week 2, Week 6, Week 12, Week 24, Week 36, Study exit

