8.3. Clinical Laboratory Analyses

Laboratory evaluations including the analyses of Chemistry laboratory tests, Hematology laboratory tests, Urinalysis, and liver function tests will be based on GSK Core Data Standards. The details of the planned displays are in [Appendix 10: List of Data Displays](#).

Clinical laboratory analyses will be by treatment group (and total for GTC1, GTC2, GTC3) and study phases (i.e., TC1, GTC1, GTC2 and GTC3, see section 11.4. Note that TC1 <= 84 days and Overall will not be included for these analyses).

Raw value and change from baseline for laboratory data will be summarized by treatment group (and total for GTC1, GTC2 and GTC3) for each visit.

Shifts from baseline relative to the normal range will be also summarized by treatment group (and total for GTC1, GTC2 and GTC3) for each visit.

Worst case urinalysis results relative to baseline for protein (category: NEG, TRA, 1+, 2+, 3+, 4+) and occult blood (category: NEG, TRA, 1+, 2+, 3+) urinalysis only will be summarized by treatment group (and total for GTC1, GTC2 and GTC3) for each study phases (TC1 and GTC1, GTC2 and GTC3). The categories for worst case are: No Change/Decreased, Any Increase, Increase to TRA, Increase to 1+, Increase to 2+, Increase to 3+, Increase to 4+. The categorization is determined by comparing the baseline category to the worst case post-baseline category. The determination of the worst case post-baseline takes into account both planned and unscheduled assessments. The percentages are based on the number of subjects in the treatment group with data for the test post-baseline. Subjects with missing baseline value are to be assumed to have normal/within range baseline value.

For Chemistry and Hematology data, the scatter plots between baseline and Week12/Withdrawal will be prepared by treatment group for TC1.

In order to provide detailed information regarding liver monitoring/stopping events which are classified as adverse events in case that these events occurred, following summary and listings (IDSL number to use) will be provided.

- Summary of Hepatobiliary Laboratory Abnormalities(LIVER10)
- Listing of Medical Conditions for Subjects with Liver Stopping Events (MH2)
- Listing of Substance Use for Subjects with Liver Stopping Events (SU2)
- Listing of Liver Monitoring/Stopping Event Reporting(LIVER5)
- Listing of Liver Stopping Event Information for RUCAM Score(LIVER6)
- Listing of Liver Biopsy Details(LIVER7)

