8.5.1. Post Void Residual (PVR) Urine Volume

PVR will only be measured in non-catheterizing subjects, or those with “mixed” patterns (ie, they do both CIC and spontaneous voiding). Therefore, analyses for PVR will include only subjects with Mixed (catheterization and spontaneous void), Spontaneous void only, Mixed (Intermittent balloon catheter and spontaneous void) or Mixed (CIC, Intermittent balloon catheter and spontaneous void)

Summary statistics and listing will be provided for PVR urine volume and its change from baseline.

Listing of PVR data will be produced. This listing will include the following items.

- Site ID, Subject ID, Treatment group, Visit, Date, Study day, PVR value, Change from baseline in PVR, Flag at initiating CIC

Flag at initiating CIC will be marked ONLY for subjects with “Spontaneous void only” or “Intermittent balloon catheter and spontaneous void” as void pattern. This flag will set to PVR data at the time of initiation of CIC (with the reason for urinary retention or elevated PVR) or 2 weeks prior to CIC if not available at the time of initiation.

Note that use of CIC includes use of indwelling catheter, if exists. The reason to use CIC are urinary retention, elevated PVR or other. Only data of use of CIC with the reason for urinary retention or elevated PVR will be used for any analyses.

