Table below shows the assessment window which applied to safety data at week 48 visit and withdrawal visit. Safety data at week 48 visit or withdrawal visit will be used as data of the visit within an assessment window, only if safety data for the planed scheduled visit is missing.

This assessment window will not be applied to any safety data at other visits. This means safety data except for week 48 visit and withdrawal visit will be only used as visit collected in eCRF.

Note that as described in section section 8, safety data at last visit (typically, this is week 48 visit or withdrawal visit) will be also treated as study exit.

Rationale: For example, if a given subject receive 2nd treatment at week 36 after 1st treatment and complete study (i.e., complete week 48 visit), data for week 48 visit will be entered in “Week 48” page in eCRF, not in “Week 12 from 2nd treatment” page. In this case, data for week 12 from 2nd treatment seems to be missing in eCRF, but this is not true. This is the case for other situations. In order to summarize safety data at week 48 visit or withdrawal visit appropriately in a given TC or GTCs, this assessment window is needed.

Analysis Set / Domain	Parameter (if applicable)	Target Number of Days from Day 1 in each TC/GTC	Analysis Window		Analysis Timepoint in appropriate study phase (TC1 or GTCs)
			Beginning Timepoint	Ending Timepoint	
e.g. “Safety”, “Efficacy” or list specific domains if required	e.g. “All” or list specific parameters (i.e. tests) if required	The target or most desired relative day or relative time value for a given visit. e.g. “Day 7”	e.g. “Day 1”	e.g. “Day 10”	e.g. VISIT 1
Safety		Day 15	Day 12	Day 18	Week 2
Safety		Day 43	Day 36	Day 50	Week 6
Safety		Day 85	Day 78	Day 92	Week 12
Safety		Day 127	Day 120	Day 134	Week 18
Safety		Day 169	Day 162	Day 176	Week 24
Safety		Day 211	Day 204	Day 218	Week 30
Safety		Day 253	Day 246	Day 260	Week 36
Safety		Day 295	Day 288	Day 302	Week 42

Analysis Set / Domain	Parameter (if applicable)	Target Number of Days from Day 1 in each TC/GTC	Analysis Window		Analysis Timepoint in appropriate study phase (TC1 or GTCs)
			Beginning Timepoint	Ending Timepoint	
Safety		Day 337	Day 330	Day 343	Week 48

NOTES :

- Day 1 is the treatment date in each TC/GTC

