11.5.2. Reporting Standards

General

 The current GSK Integrated Data Standards Library (IDSL) will be applied for reporting, unless otherwise stated (IDSL Standards Location: https://spope.gsk.com/sites/IDSLLibrary/SitePages/Home.aspx): 
 4.03 to 4.23: General Principles 5.01 to 5.08: Principles Related to Data Listings 6.01 to 6.11: Principles Related to Summary Tables 7.01 to 7.13: Principles Related to Graphics Do not include subject level listings in the main body of the GSK Clinical Study Report. All subject level listings should be located in the modular appendices as ICH or non-ICH listings
Formats

 GSK IDSL Statistical Principles (5.03 & 6.06.3) for decimal places (DP's) will be adopted for reporting of data based on the raw data collected, unless otherwise stated. Numeric data will be reported at the precision collected on the eCRF. The reported precision from non eCRF sources will follow the IDSL statistical principles but may be adjusted to a clinically interpretable number of DP's.
Planned and Actual Time

 Reporting for tables, figures and formal statistical analyses: 
 Planned time relative to dosing will be used in figures, summaries, statistical analyses and calculation of any derived parameters, unless otherwise stated. The impact of any major deviation from the planned assessment times and/or scheduled visit days on the analyses and interpretation of the results will be assessed as appropriate. Reporting for Data Listings: 
 Planned and actual time relative to study drug dosing will be shown in listings (Refer to IDSL Statistical Principle 5.05.1). Unscheduled or unplanned readings will be presented within the subject's listings.
Unscheduled Visits

 Unscheduled visits will not be included in summary tables and/or figures. All unscheduled visits will be included in listings.

Descriptive Summary Statistics	
Continuous Data	Refer to IDSL Statistical Principle 6.06.1 N, mean, standard deviation (or standard error), median, minimum, maximum.
Categorical Data	N, n, frequency, %
Graphical Displays	

• Refer to IDSL Statistical Principals 7.01 to 7.13.	

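### The TC1 PVR tables and by-visit chemistry tables omit protocol-triggered follow-up visits, and no maximum post-baseline PVR is summarised

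*SAP*

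**What the plan says.** **The exclusion.** SAP section 8 states the rule for safety data: "Safety data from unscheduled visit will not be included in safety analysis (but included in listing"). SAP 11.5.2 states it for all outputs: "Unscheduled visits will not be included in summary tables and/or figures". SAP 11.3.2 re-slots safety data only from the Week 48 and withdrawal visits; otherwise, "This assessment window will not be applied to any safety data at other visits".

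**What is tabulated.** SAP 8.5.1 plans the following for PVR: "Summary statistics and listing will be provided for PVR urine volume and its change from baseline". These are Tables 3.100 and 3.101, for TC1 only, produced at interim and final. SAP section 8 shows TC1 PVR at baseline, Weeks 2, 6, 12, 24 and 36 and study exit. It shows TC1 chemistry at baseline, Week 12 and study exit.

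**The triggered visits.** Under protocol 7.4.7, if PVR is 200 to <350 mL and CIC is not started, "the subject will be seen at an additional visit 1 week later, when the PVR and any associated symptoms will be reassessed". A further visit follows a week later if PVR is still rising, and one-week visits follow the start and the stop of CIC. Under protocol Appendix 2, once ALT is at least 3xULN without a stopping event, "Subject must return weekly for repeat liver chemistries".

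**The exception.** For urinalysis protein and occult blood, SAP 8.3 says: "The determination of the worst case post-baseline takes into account both planned and unscheduled assessments".

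**The concern.** The omitted visits are not a random subset. They exist because the preceding value was raised, so they are where PVR may first pass 350 mL or ALT may climb further. A by-visit table that drops them describes values at planned visits. That is a fair question, but it is not the same as the highest value each subject reached, and for PVR no other table answers the second question.

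Any loss would be expected mainly on active. Protocol 4.6.1 gives first-treatment urinary retention of 17.2% on 200 U against 2.9% on placebo in the overseas studies. Those figures suggest a direction only; they do not size the effect here. The interim version of these tables is intended for the regulatory submission. The primary endpoint is not touched.

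**Working it through.** The plan states no figure on this point, so the check compares the passages and the visit days.

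**1. Are the triggered visits unscheduled?** The SAP does not define the term. Protocol 7.4.6.2 sets the additional follow-up visit apart from scheduled visits, and protocol 7.4.7 speaks of a raised PVR at either a scheduled or an unscheduled visit. The Time and Events tables have no column for these visits. Treating them as unscheduled is an assumption, but a well-supported one.

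**2. Could they enter a table through a window?** Day = target day + 7 per week of delay. The windows are those of SAP 11.3.2.

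| Trigger visit | Target day | +1 week | +2 weeks | Own window |
|---|---|---|---|---|
| Week 2 | 15 | 22 | 29 | 12-18 |
| Week 6 | 43 | 50 | 57 | 36-50 |
| Week 12 | 85 | 92 | 99 | 78-92 |
| Week 24 | 169 | 176 | 183 | 162-176 |
| Week 36 | 253 | 260 | 267 | 246-260 |

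Days 22 and 29 fall between the Week 2 and Week 6 windows. One-week re-checks after Weeks 6, 12, 24 and 36 land on the last day of a window, but SAP 11.3.2 does not apply windows to such visits. Weekly ALT repeats after Week 12 fall on Days 92, 99, 106 and 113, and none enters by this route.

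**3. Illustration for PVR (assumed values).** A subject has 250 mL at Week 2, 380 mL at the additional visit on Day 22, and 150 mL at Week 6. Table 3.100 receives 250 and 150. The highest tabulated value is 250 mL against 380 mL reached, a gap of 380 - 250 = 130 mL. The gap in change from baseline is also 130 mL, whatever the baseline. The maximum listed among the SAP 11.5.2 descriptive statistics does not help, because it is the maximum across subjects at one planned visit.

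**4. Illustration for ALT.** ALT is 3 to <5xULN at Week 12, 5 to <8xULN at one weekly repeat, then settles before the persistence criteria in Appendix 2 are met. If there are no symptoms and bilirubin stays below 2xULN, no stopping event occurs. The by-visit value and change rows hold Week 12 and study exit only.

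**5. What else in the SAP bears on this?**
- SAP 8.3 counts unscheduled values in one safety summary, which conflicts with the flat wording of sections 8 and 11.5.2.
- SAP 11.6.1 refers to a laboratory row covering any post-baseline visit. It does not say whether unscheduled visits count.
- Table 3.93 (hepatobiliary abnormalities) has no stated data rule. A literal reading of 11.5.2 would exclude unscheduled values. Yet Appendix 12 keeps laboratory records dated within a liver event for the interim data.
- Protocol 9.4.2 specifies, by visit, the proportion of patients changing PVR category (<100, 100 to <200, 200 to <350, at least 350 mL). SAP 6.1.3 uses these categories at baseline only. SAP Table 1, which lists departures from the protocol analysis, does not mention the omission.

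**The case against.** The strongest reply is that the rule is sound for what it governs. Protocol 9.4.2 itself asks for PVR and out-of-range laboratory values by visit, and mixing outcome-triggered repeats into visit means would distort them. That stands, and the by-visit tables should stay as they are.

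Several stronger readings are tempting, and the documents do not support them:

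- **That every safety summary loses unscheduled data.** Worst-case urinalysis does not. Adverse event tables are assigned by event start date (SAP 11.4.1.2), so urinary retention is counted in the special-interest tables whichever visit found it.
- **That ALT of 4xULN at Week 12, rising to 9xULN at a re-check, would appear only as 4xULN.** At 8xULN or above a stopping criterion is met, and protocol 5.5 calls for withdrawal. The withdrawal visit includes chemistry, and SAP section 8 reports it as study exit. That later value need not be the peak, and Appendix 2 allows the subject to stay for follow-up, so the route is not certain. In a shift table relative to the normal range, both values are simply high.
- **That the rule empties a category of 350 mL or more.** The SAP plans no post-baseline PVR categories, so none would appear even for a planned visit.
- **That Table 3.93 excludes the re-checks.** The SAP does not say.

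The reply also notes that few subjects are involved and that a listing shows them well. SAP 8.5.2 gives fewer than 5 subjects in total for the two void patterns without CIC, and Appendix 5 of the protocol is headed for subjects not catheterizing at baseline. This largely stands. However, the PVR analysis set in SAP 8.5.1 also includes mixed patterns with CIC, whose number is not given. In those subjects, retention becomes an adverse event only on progression to exclusive CIC. Otherwise a raised PVR is recorded only if judged clinically significant. Adverse event tables show occurrence and severity, not millilitres.

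**Conclusion.** The point holds in a limited form. Tables 3.100-3.101 and the by-visit chemistry summaries can miss the highest PVR or ALT when it occurs only at a protocol-triggered follow-up visit. No table gives the maximum post-baseline PVR, and the category summary in protocol 9.4.2 is absent without being declared.

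The scheduled value that triggered the visit stays in the tables, so understatement arises only when the follow-up value is higher. That is possible, not certain, and its size cannot be computed from the documents. Few subjects are affected, although in groups this small one missing peak can change the reported range. A reader might infer that safety signals are hidden. They are not: retention is counted in the adverse event tables and the individual values are listed.

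The conclusion rests on the additional visits being recorded as unscheduled. The change is a worthwhile, inexpensive improvement rather than the repair of a serious fault.

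**What to change.** 1. Keep the by-visit tables unchanged.
2. Add to the TC1 PVR tables the maximum post-baseline PVR per subject, by arm: value, change from baseline, and the four categories of protocol 9.4.2. Use planned and unscheduled assessments within TC1.
3. Amend SAP sections 8 and 11.5.2 to say that worst-case summaries use all post-baseline assessments, planned and unscheduled. Name them: urinalysis, the laboratory row for any post-baseline visit in 11.6.1, and hepatobiliary Table 3.93. This reconciles those sections with 8.3 and settles the two outputs whose data rule is now open.
4. If the by-visit PVR category summary is not restored, record that departure in SAP Table 1.

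The cost is SAP wording and a few derived rows from data already collected and listed. The counts will be small, and the reported peaks may look slightly less favourable.

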- (d) Diary must have been completed for any 3 consecutive days in the week prior to the visit (for screening phase only, it could have been completed for 3 consecutive days at any time during the screening phase). The volume voided is recorded by subjects for one 24-hour period during the 3 day diary collection period.
- (e) Only serious adverse events assessed as related to study participation or a GSK product will be recorded from the time when a subject consents
- (f) Measured only body weight
- (g) Urine culture and sensitivity is performed by the central laboratory when dipstick results are positive for nitrites or leukocyte esterase.
- (h) For patients with doubtful reaction in urinary pregnancy test, the investigator (or subinvestigator) may conduct serum pregnancy test.
- (i) For patients without a UTI as determined from the urinalysis or urine culture and/or investigator opinion, prophylactic antibiotic are to be administered 1 to 3 days before study treatment, on the day of treatment, and 1 to 3 days after treatment. For patients with a UTI as determined from the urinalysis or urine culture and/or investigator opinion, an antibiotic to which the identified organism is sensitive is to be administered at least 5 days prior to study treatment and continued for at least 3 days following the procedure.
- (j) If qualification for re-treatment criteria was met, the patient will undergo the exams specified in Table 2, column marked "If qualification for re-treatment criteria was met".
- (k) Patients who are not re-treated will remain in Treatment phase 1 and continue to visit at the scheduled study visit.
- (l) Patients who are using the medications or therapies urinary incontinence due to NDO should maintain the same dose from at least 7 days before the start of the screening phase throughout Treatment phase 1.
- (m) Samples may be collected during the screening period through Day 1 (prior to randomization)

**Table 2 Time and Events Table [Treatment phase 1 (if qualification for re-treatment criteria was met) to treatment phase 2]**

	Treatment phase 1	Treatment phase 2															
Week	If qualification for re-treatment criteria was met (Within 21 days prior to re-treatment)	1st re-treatment	Re-treatment (1st)							2nd re-treatment	Re-treatment (2nd)					Withdrawal	

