5.2. Baseline Definitions

For all endpoints (except as noted in baseline definitions) the baseline value will be the latest pre-dose assessment with a non-missing value, including those from unscheduled visits. For urinary diary data, the baseline value will be the latest pre-dose 3-day diary which has at least one valid diary day. If time is not collected, Day 1 assessments are assumed to be taken prior to first dose and used as baseline. This baseline means “study baseline”. “Study baseline” will be used for all analyses using baseline data (e.g., change from baseline).

Unless otherwise stated, if baseline data is missing no derivation will be performed and baseline will be set to missing.

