	GTC2	Qualification for GTC2, Week 2, Week 6, Week 12, Week 24, Study exit
	GTC3	Qualification for GTC3, Week 2, Week 6, Week 12, Study exit

NOTES:

- Baseline means study baseline defined as [5.2](#).
- Study baseline will be used for the derivation of change from baseline
- Urinalysis results will be displayed by using worst case results post-baseline relative to baseline for protein and occult blood urinalysis only in accordance with IDSL standards rationale, not by visit
- Study exit includes withdrawal.
- [1]: only for subjects with Placebo at TC 1

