GTC2	Study Exit or Withdraw in TC2	Study Exit / Withdraw Date	2nd treatment date																													
GTC2	Receive next treatment	Date prior to 3rd treatment	2nd treatment date																													
GTC3	All subjects in GTC3	Study Exit / Withdraw Date	3rd treatment date																													

For subjects who received Placebo as first treatment
																																

Duration of Follow-Up instead of Extent of Exposure

Overall / TC for calculation	Subject status	X	Y
Overall	All subjects	Study Exit / Withdraw Date	2nd treatment date (1st treatment date of GSK1358820)
TC1	Study Exit or Withdraw in TC1	Study Exit / Withdraw Date [1]	1st treatment date
TC1	Receive next treatment	Date prior to 2nd treatment [1]	1st treatment date
GTC1	Study Exit or Withdraw in GTC1	Study Exit / Withdraw Date	2nd treatment date (1st treatment date of GSK1358820)
GTC1	Receive next treatment	Date prior to 3rd treatment	2nd treatment date (1st treatment date of GSK1358820)
GTC2	All subjects in GTC2	Study Exit / Withdraw Date	3rd treatment date (2nd treatment date of GSK1358820)
GTC3	Not applicable, because GSK1358820 treatment is allowed only two times for subjects who received Placebo as first treatment in this study.		

- [1] In interim analysis, use the following date:
 - Date of withdraw date for subjects who do not receive 2nd treatment and withdraw before week 24 after 1st treatment
 - Date of the Week 24 visit in treatment phase 1 for subjects who do not receive 2nd treatment and do not withdraw
 - Date prior to 2nd treatment for subjects who receive 2nd treatment at the Week 12 / 18 visit in treatment phase 1.

Duration of NDO history

- Duration of NDO history is defined as the duration (years) from the date of diagnosis to the date of screening visit.

Identification of anticholinergic drug and beta-3 agonist

- Since information of anticholinergic drug and beta-3 agonist was collected as 'prior NDO medication', it is needed to identify which codes will be regarded as anticholinergic drug and beta-3 agonist. Following code will be in SI dataset

Drug	Term Name	Code
Anticholinergics	FESOTERODINE	54026501
	FESOTERODINE FUMARATE	54026502
	IMIDAFENACIN	53735601
	OXYBUTYNIN	00538901
	OXYBUTYNIN HYDROCHLORIDE	00538902
	PROPIVERINE	01241601
	PROPIVERINE HYDROCHLORIDE	01241602
	SOLIFENACIN	53085701
	SOLIFENACIN SUCCINATE	53085702
	TOLTERODINE	01350201
	TOLTERODINE TARTRATE	01350202
	TOLTERODINE FUMARATE	01350203

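### Placebo-first subjects' GTC change, shift and worst-case urinalysis are measured from before placebo; this matters mainly for Table 3.92 and the pooled Total and shift rows

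*SAP*

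**What the plan says.** SAP 5.2 defines baseline once: "the baseline value will be the latest pre-dose assessment with a non-missing value, including those from unscheduled visits". The dose meant is the first study dose, since where no time is recorded "Day 1 assessments are assumed to be taken prior to first dose and used as baseline". The same section calls this study baseline and says that it "will be used for all analyses using baseline data (e.g., change from baseline"). The notes to the visit table in SAP 8 repeat the rule for safety: "Study baseline will be used for the derivation of change from baseline". Neither document defines a cycle-specific or pre-GSK1358820 baseline.

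For placebo-first subjects the cycle clock does move. SAP 11.4.1.2 starts their GTC1 adverse-event period at the 2nd treatment. SAP 11.6.2 counts their GTC1 follow-up from the "2nd treatment date (1st treatment date of GSK1358820"). SAP 11.3.2 sets Day 1 to the treatment date of each cycle.

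Protocol 7.1, Table 2, has a column headed "If qualification for re-treatment criteria was met (Within 21 days prior to re-treatment"). Chemistry, hematology, vital signs and urinalysis are all marked there. Vital signs and urinalysis are repeated on the re-treatment day, before injection.

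The SAP displays these values. For chemistry, hematology and ECG the GTC1 rows are "Study baseline, Qualification for GTC1 [1], Week 12, Study exit", and the Qualification row applies only to subjects given placebo first. Vital signs also have a pre-injection Week 0 row. GTC summaries are by original treatment group and in total.

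For urinalysis protein and occult blood, SAP 8.3 says: "The categorization is determined by comparing the baseline category to the worst case post-baseline category". SAP 8 notes that this display is not by visit.

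**The concern.** GTC1 is meant to describe the first exposure to GSK1358820. For active-first subjects, study baseline is the value just before that exposure. For placebo-first subjects it lies a whole placebo cycle earlier. The Total column therefore combines two quantities under one label: change since the first active injection, and change since before placebo.

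Errors can go either way. An abnormality that arose on placebo and persisted is scored as a shift, or as an Any Increase urinalysis result, in the first active cycle. One that was present at study entry, cleared during placebo and returned after the first active injection is scored as no change. Safety of single and repeated GSK1358820 treatment is a stated objective, and with about 15 subjects per arm one misplaced subject is visible in a percentage. GTC2 for placebo-first subjects has the same reference and the same problem.

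**Working it through.** The plan gives no figure on this point to reproduce, and its sample-size figures play no part. The check compares definitions and does date arithmetic.

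**1. What is reported.** For one subject let B0 be study baseline, B1 the last value before the first GSK1358820 injection, and Y a GTC1 value after it.

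Reported change = Y − B0 = (B1 − B0) + (Y − B1)

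- Active-first: B1 = B0, so the first term is zero.
- Placebo-first: the first term is the drift over the placebo cycle.

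I take GTC1 for laboratory and vital-sign data to start at the same injection as for adverse events.

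**2. Age of the reference at the first active injection (placebo-first).** Inputs: re-treatment no earlier than 84 days after the previous treatment and no later than 36 weeks after the first (Protocol 5.3); screening within 28 days before first treatment (Protocol 7.1, Table 1).

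- Shortest: 12 × 7 = 84 days.
- Longest, baseline on Day 1: 36 × 7 = 252 days. This is the normal limit for vital signs and urinalysis, which are repeated at Week 0 before treatment.
- Longest, baseline at screening: 252 + 28 = 280 days. This applies to chemistry and hematology, scheduled before treatment only at screening.
- Available alternative: at most 21 days (qualification), or the same day for vital signs and urinalysis.

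**3. Weight in the GTC1 Total.** Let m be the number of placebo subjects re-treated. The documents do not give m, so the values below are assumptions. If all 15 active-first subjects contribute, the placebo-first share is m/(15 + m), and the mean change in Total includes that share of the mean placebo-period drift. One subject is 1/(15 + m) of Total and 1/m of the Placebo / GSK1358820 column.

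| m | Share of Total | One subject, Total | One subject, own column |
|---|---|---|---|
| 5 | 5/20 = 25% | 1/20 = 5.0% | 1/5 = 20% |
| 10 | 10/25 = 40% | 1/25 = 4.0% | 1/10 = 10% |
| 15 | 15/30 = 50% | 1/30 = 3.3% | 1/15 = 6.7% |

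**4. Which displays are affected (SAP 11.10.8).**

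| GTC tables | By visit, with Qualification row? | What remains uncorrected |
|---|---|---|
| 3.82, 3.88, 3.99 (change: chemistry, hematology, vital signs) | Yes | Post-dose Total |
| 3.84, 3.90 (normal-range shift) | Yes | Post-dose shift rows and Total |
| 3.92 (worst-case urinalysis) | No | Own column and Total |

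**5. Table 3.92, two constructed cases.**

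- Protein negative at study baseline, 1+ at qualification, worst value 1+ after the first active injection: scored as Any Increase. From the qualification value there is no change.
- Protein 1+ at study baseline, negative at qualification, worst value 1+ after the first active injection: scored as no change. From the qualification value it is an increase to 1+.

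**The case against.** The strongest reply is that the display plan already exposes the placebo period. SAP 8.3 and 8.4 summarise change from baseline for each visit, and shifts too for laboratory data. Placebo-first subjects have their own column and a Qualification row, so drift that arose on placebo appears before any GSK1358820 is given, and the group's mean change on drug can be read as a difference between rows. A reader might infer from the baseline rule that placebo-period changes are passed off as drug effects throughout the GTC tables. The documents do not support that for the by-visit displays.

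This reply does not reach three places. Table 3.92 has no visit rows. The post-dose Total still mixes the two references. Separate shift rows do not show which subjects moved between qualification and Week 12.

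Second, attribution of clinically significant abnormalities does not depend on this baseline: they are recorded as adverse events and assigned to a cycle by start date. Listing 30 also gives laboratory data for every subject with an out-of-range value. Both points stand and limit the harm. However, the listing leaves the summary tables as they are, and the display list has no vital-signs listing.

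Third, a single baseline is explicit and consistent and shows cumulative change from a state before any study injection. The alternative value for placebo-first subjects follows a placebo injection procedure, which could matter for occult blood. That is a reason to disclose the difference and keep study baseline on display. It does not justify scoring a urinalysis increase that arose on placebo as an increase in the first active cycle.

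**Conclusion.** The point holds, with modest impact. For placebo-first subjects, GTC1 and GTC2 change, normal-range shift and worst-case urinalysis use a reference 84 to 252 days old at the first active injection (up to about 280 for screening-only laboratory tests), when one at most 21 days old exists. The uncorrected effect is mainly on Table 3.92, and on the post-dose Total and shift rows of Tables 3.82, 3.84, 3.88, 3.90 and 3.99.

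A reader might go further and conclude that first-exposure safety reporting as a whole is compromised, or that half of the subjects in it are misclassified. The documents support neither. Adverse-event tables are assigned by start date, ECG is summarised as findings rather than change, PVR summary tables cover only the double-blind cycle, and TC1 and efficacy are untouched. The 50% share is the upper end of an assumed range of 25% to 50%, reached only if all 15 placebo subjects are re-treated. It counts subjects whose reference is old, not subjects whose result is wrong: a result changes only where the value moved during placebo. The documents give no information on how often that happens.

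**What to change.** In SAP 5.2 and section 8, define a GSK1358820 baseline: the last non-missing value before the first GSK1358820 injection. For active-first subjects it equals study baseline. For placebo-first subjects it is the qualification value or, for vital signs and urinalysis, the pre-injection value on the re-treatment day.

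Use it for the GTC worst-case urinalysis table (3.92) and for the GTC change and shift summaries, including Total (3.82, 3.84, 3.88, 3.90, 3.99). Keep study baseline for TC1 and efficacy, and keep the study-baseline row in the GTC displays.

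The cost is SAP wording, one derived flag and a footnote. No new data are needed, and the affected tables are scheduled only for the final report, so no interim output changes. The drawback is that placebo-first subjects then have two baselines, the second taken after a placebo injection procedure. The footnote should say so.
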